5.3.3 Exclusion Criteria

1. Subject has another implanted device (active or passive implanted device) that prohibits safe scanning.

- 2. Subject has previously experienced an MRI-related adverse event or cannot undergo MRI for any other reason.
- 3. Subject is pregnant or nursing, or plans to become pregnant during the clinical investigation follow-up period.
- 4. Subject has other anatomic or comorbid conditions, or other medical, social, or psychological conditions that, in the investigator's opinion, could limit the subject's ability to participate in the clinical investigation or to comply with follow-up requirements, or impact the scientific soundness of the clinical investigation results.
- 5. Subject is currently participating in another clinical investigation that may confound the results of this study.

5.4 Subject Enrollment

A patient is considered enrolled in the clinical investigation from the time the patient provides written informed consent.

5.5 Subject Withdrawal

Each enrolled subject shall remain in the clinical investigation until completion of the required follow-up period; however, a subject's participation in any clinical investigation is voluntary and the subject has the right to withdraw at any time without penalty or loss of benefit. Conceivable reasons for discontinuation may include, but not be limited to, the following:

- Subject death (cause must be documented)
- Subject does not meet the inclusion/exclusion criteria and does not require additional follow-up
- Subject voluntary withdrawal
- Subject non-compliance
- Subject's participation is terminated by the PI or co-investigator
- Subject lost-to follow-up as described below
- Subject's follow-up is terminated according to Section 3.3.

The Sponsor must be notified of the reason(s) for subject discontinuation. The site will provide this information to the Sponsor. Investigators must also report this to their respective IRB/EC as defined by their institution's procedure(s).

No additional follow-up will be required or data recorded from subjects once withdrawn from the clinical investigation, except for the status (deceased/alive) at the time of withdrawal, if not previously collected.

However, if a subject withdraws from the investigation due to problems related to the safety or performance of the device under investigation, the investigator shall ask for the subject's permission to follow his/her status/condition outside of the clinical investigation as appropriate.

Lost-to-Follow-up

A subject is considered lost-to-follow-up if the subject does not adhere to the scheduled follow-up visit but has not explicitly requested to be withdrawn from the clinically study. Site personnel shall make all

reasonable efforts to locate and communicate with the subject (and document these efforts in the source documents), including the following, at each contact time point:

- A minimum of two telephone calls on different days over the specified follow-up windows to contact the subject should be recorded in the source documentation, including date, time and initials of site personnel trying to make contact.
- If these attempts are unsuccessful, a letter (certified if applicable) should be sent to the subject.
- If a subject misses the follow-up contact time point, it will be considered a missed visit. If the
 subject misses their 1-month follow-up visit and the above-mentioned attempts at communicating
 with the subject are unsuccessful, the subject will be considered lost-to-follow-up.

Note: Telephone contact with General Practitioner, non-clinical investigation neurologist or relative without the presence of the subject or indirect documentation obtained via discharge letters will not be considered as subject contact.

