5.8 Number of Subjects

To support the safety of the Infinity DBS system with MR Conditional labeling, up to 74 subjects will be enrolled in this study. Approximately 35 subjects will be included in each device configuration group (Leads Only and Full System). The total number of enrolled subjects assumes a 5% attrition rate following enrollment (e.g., due to subject unwilling to undergo DBS implant procedure, or for any other reason). Data from only one MRI procedure for each subject will be collected.

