7.4 Adverse Event

7.4.1 Adverse Event Reporting

General AE Reporting

Safety surveillance and reporting starts as soon as the patient is enrolled in the clinical investigation. Safety surveillance and reporting will continue until the one month follow-up visit has been performed, the subject is deceased, the subject concludes participation in the clinical investigation or the subject withdraws from the clinical investigation, whichever comes first. All adverse event data will be collected throughout the time period defined above and will be reported to the Sponsor on a CRF. Additional information with regard to an adverse event should be updated within the appropriate CRF.

Unchanged, chronic, non-worsening or pre-existing conditions are not AEs and should not be reported.

An offline form will be made available to allow the investigator to report SAEs in the event the entry cannot be made in the electronic data capture (EDC) system. This does not replace the EDC reporting system. All information must still be entered in the EDC system as soon as feasible.

SAE Reporting

The investigator should report all SAEs to the Sponsor as soon as possible but no later than outlined below.

Clinical Site	Reporting timelines
All Sites	SAEs must be reported to the Sponsor no later than 3 calendar days from the
	day the site personnel became aware of the event or as per the site's local
	requirements, if more stringent than 3 calendar datys.

The date the site staff became aware the event met the criteria of an SAE must be recorded in the source document. The Investigator will further report the SAE to the local IRB/EC according to the local IRB/EC reporting requirements.

Reportable events to the sponsor are considered:

- All serious adverse events regardless of relatedness to the device and/or implant procedure
- All device- or implant procedure-related adverse events
- All MRI-related adverse events

Refer to the specific device manuals for the adverse events that are associated with implanting or using the neurostimulation system for DBS and for MRI related adverse events.

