8.2 Statistical Analyses

8.2.1 Primary Endpoint Analysis

The primary endpoint is the event rate of MRI-related adverse events through 1 month post-MRI procedure. The clinical acceptance criterion for the rate of MRI-related adverse events is 7%, drawn from historical rates of significant adverse events in DBS studies. The endpoint will be evaluated for each group and will be reported as the percentage of subjects experiencing the events. The clinical acceptance criterion must be satisfied in both groups (leads-only and full system).

The primary analysis will be conducted on subjects who meet all of the following criteria:

• Signed informed consent

- Met the MRI procedure eligibility requirements at the time of the MRI procedure (as per the MRI Procedure Clinician's manual)
- Had a study MRI procedure

Any adverse event will be included in the primary endpoint analysis if it:

- 1. Is classified as being MRI-related (as determined by the CEC), occurs during or after the MRI procedure, and cannot be attributed to any other cause; **and**
- 2. Is classified as being related to the device (implanted or external component) (as determined by the Investigator); **and**
- 3. Meets the criteria for serious adverse event **or** is a non-serious adverse event that is the result of irrecoverable failure of therapy delivery or device communication.

Examples of MRI-related adverse events that will be included in the primary endpoint analysis are:

- Symptomatic intracranial hemorrhage that cannot be attributed to the implant procedure.
- New and permanent neurological symptoms that cannot be attributed to a cause other than the MRI procedure.
- Lack of therapeutic benefit due to damage to the IPG requiring device replacement (e.g., stimulation cannot be turned on following the MRI procedure, stimulation cannot be adjusted following the MRI procedure).

Examples of adverse events that may be reported but will not be included in the primary analysis are:

- Transient, non-serious complications such as sensory or motor disturbance during the MRI procedure that may result from induced currents on leads.
- Sensation of warmth at the IPG that resolves following the MRI procedure.
- Pain around the implanted IPG site that could be related to the implant procedure.

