# 2.3 Endpoint Analysis

# 2.3.1 Primary Endpoint

The primary endpoint is the event rate of MRI-related adverse events through post-MRI procedure.

Any adverse event will be included in the primary endpoint analysis if it:

- Is classified as being MRI-related (as determined by the CEC), occurs during or after the MRI procedure, and cannot be attributed to any other cause; **and**
- Is classified as being related to the device (implanted or external component) (as determined by the Investigator); **and**
- Meets the criteria for serious adverse event **or** is a non-serious adverse event that is the result of irrecoverable failure of therapy delivery or device communication.

The clinical acceptance criterion for the rate of MRI-related adverse events is 7%,

The primary analysis will be performed on Primary Analysis Population. The primary endpoint will be summarized as number of events, number of subjects who experienced these events and percentage. The clinical acceptance criterion is satisfied if the event rate is less than 7% in both groups (leads-only and full system).

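### After a scanned subject leaves early, a harm that first qualifies before 1 month is not recorded, and one such subject can turn a failing group into a passing one

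*Protocol*

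**What the plan says.** **Follow-up after exit.** Protocol 5.5 states: "No additional follow-up will be required or data recorded from subjects once withdrawn from the clinical investigation". The only item still collected is whether the subject was alive or dead at that time. There is one special provision, for withdrawal over device safety or performance: "the investigator shall ask for the subject's permission to follow his/her status/condition outside of the clinical investigation as appropriate". The reasons for discontinuation listed in 5.5 also include non-compliance and termination by the investigator. Neither is a withdrawal of consent, and the special provision, which concerns subjects who withdraw over a device problem, is not written for them.

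**Adverse event reporting.** Under protocol 7.4.1, surveillance runs until the 1-month visit, death, or "the subject concludes participation in the clinical investigation or the subject withdraws from the clinical investigation, whichever comes first". All adverse events within that period go on a CRF.

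**Endpoint.** Protocol 8.2.1 states: "The primary endpoint is the event rate of MRI-related adverse events through 1 month post-MRI procedure". It "will be reported as the percentage of subjects experiencing the events", by group. An event counts only if it is MRI-related as judged by the CEC, device-related as judged by the investigator, and either serious or an irrecoverable failure of therapy delivery or device communication. The population requires consent, MRI eligibility at the scan and a study MRI. Completed follow-up is not required.

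**Decision rule.** SAP 2.3.1: "The clinical acceptance criterion is satisfied if the event rate is less than 7% in both groups".

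**Missing data.** There is no imputation (protocol 8.6, SAP 2.9) and no sensitivity analysis (SAP 2.13). SAP 3.3 summarises the reasons for early termination, not the outcomes of those subjects.

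**The concern.** The endpoint has a 1-month window, but observation can end sooner for the subjects in whom it matters most. In the case that 5.5 itself describes, a safety or performance problem prompts the exit and the exit ends the count. In an open-label study the investigator can also end participation.

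Some qualifying events take time to qualify. Two of the examples in 8.2.1 depend on permanence of neurological symptoms or on a need to replace the device, and either may become clear only after the subject has left. If so, the study record stays as it was on the day of exit.

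Such a subject adds nothing to the numerator and remains in the denominator. The error can only lower the observed rate, and no planned analysis would show it.

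**Working it through.** **Inputs**
- Acceptance rule: observed rate below 7% in each group (SAP 2.3.1; protocol 8.2.1)
- Group size: about 35 per configuration, 70 in total (protocol 5.8)
- Attrition: 5% after enrolment; the one example named is a subject unwilling to have the implant (protocol 5.8)
- Post-scan exits: not given

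**1. The plan's own figure.** Protocol 5.8 says "up to 74 subjects will be enrolled in this study". 70 / 0.95 = 73.7, rounded up to 74. This reproduces. The basis for 35 per group cannot be checked, because the sample size sections are empty in the public text.

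**2. The rule as whole subjects.** 0.07 × 35 = 2.45, so at most two subjects with an event may be seen.

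| Subjects with an event | Rate, n = 35 | Result |
|---|---|---|
| 1 | 2.86% | pass |
| 2 | 5.71% | pass |
| 3 | 8.57% | fail |

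The boundary is the same for n = 33 to 37: two pass (6.06% to 5.41%) and three fail (9.09% to 8.11%). One unrecorded event is worth 1/35 = 2.86 points and can move a group from fail to pass.

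**3. How many subjects could be affected.** 74 × 0.05 = 3.7, or about 2 per group, if all the planned attrition fell after the scan. The named example falls before it, so 0 to 2 per group is an assumed range.

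**4. Effect on the chance of passing.** For one group, P(pass) = P(X ≤ 2). All true rates and loss fractions below are assumed.

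(a) Exits linked to harm, so that a fraction m of qualifying events is lost: X ~ Bin(35, p(1 − m)).

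| True rate p | m = 0 | m = 0.25 | m = 0.50 |
|---|---|---|---|
| 7% | 0.552 | 0.722 | 0.877 |
| 10% | 0.306 | 0.506 | 0.746 |

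(b) Exits unrelated to harm, with w average-risk subjects unobserved for the whole window: X ~ Bin(35 − w, p). At p = 10%, P(pass) is 0.306 for w = 0, 0.326 for w = 1, 0.346 for w = 2 and 0.389 for w = 4.

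Ordinary attrition therefore does little. A large effect needs exits linked to harm, and the loss fractions in (a) are deliberately wide.

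**5. Worst case.** Count scanned exits with unknown 1-month status as events (n = 35). Two observed plus one unknown, one plus two, and none plus three all give 3/35 = 8.57%, a fail.

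**The case against.** A reader might infer that any harm still evolving at exit is lost to the 7% count. The documents do not support that. Under 7.4.1 all adverse events up to exit go on a CRF, and an event that by then is serious or an irrecoverable failure, and meets the two relatedness criteria, counts. The same section asks for adverse event information to be updated and does not say whether this stops at withdrawal. The statement in 5.5 that no data are recorded after withdrawal points the other way, so the two should be reconciled. What remains exposed is a harm that starts or first qualifies after exit.

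Other objections carry weight:
- **Device failures are partly caught on the day.** Protocol 6.3.2 checks stimulation, amplitude adjustment and interrogation immediately after the scan in the full system group. A gross IPG failure would normally be seen then. Later deterioration or a late neurological harm would not.
- **The decisive case is narrow.** It needs two counted events in a group and a third subject who leaves after the scan and qualifies only afterwards. Nothing in the documents makes this likely. With so low a limit, though, it need happen only once.
- **The denominator is not fully visible.** The SAP 2.1.1 population sentence is blacked out, so the reading rests on protocol 8.2.1.
- **Protocol 6.1 is not a full precedent.** Scanned subjects later found ineligible are followed to 1 month, but they have not withdrawn. This shows that follow-up off the normal path is feasible, not that it may continue without consent.
- **Permission to be followed outside the study is not consent to study data.** This stands, and it shapes the fix. The consent form and CEC charter are not in the public text and may already say more.

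**Conclusion.** The point holds in a limited form. A scanned subject who withdraws over a device safety or performance problem, or whose participation ends for non-compliance or by investigator decision, has no study data recorded after exit. A harm that starts, or first becomes serious, permanent or irrecoverable, between exit and 1 month is missed, and the subject is counted as event-free.

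One such subject can change a group's result from 3/35 = 8.6% to 2/35 = 5.7%. Both groups must pass, so it can change the study's result. The direction rests on the population text in protocol 8.2.1. The frequency is unknown and probably small. A reader might take the larger shifts in pass probability as a forecast, but they depend on assumed losses of 25% to 50% of events that the documents do not support. This is a cheap improvement, not a flaw that undermines the design.

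**What to change.** The change concerns data capture only and leaves clinical care as it is. For subjects who have had the study MRI:

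1. **Exits without withdrawal of consent.** State in protocol 5.5 and 7.4.1 that non-compliance or investigator termination ends study visits, but that adverse event and device-status recording continues through 1 month after the scan unless the subject withdraws consent to data collection.
2. **Safety or performance withdrawals.** Ask for explicit consent, with a matching sentence in the consent form, to record 1-month adverse event and device status on the study CRFs. Send these events to the CEC and count those that qualify in the primary endpoint.
3. **Adverse event updates.** Say in 7.4.1 whether updating of events reported before exit continues afterwards, and align this with 5.5.
4. **SAP.** In 3.3, list post-scan exits by group with reason and last known event status. In 2.13, add one worst-case analysis that counts scanned exits with unknown 1-month status as events. Report it beside the primary result, not in place of it.

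The cost is a protocol and consent-form amendment with the usual ethics review, CRF entries for probably a few subjects, and one extra table. Some subjects may refuse, and for them only the worst-case analysis helps. The sponsor also accepts a possibly less favourable rate.

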6.4 Follow-up Assessments

6.4.1 1 Month Post-MRI Procedure Follow-up (In clinic)

The only follow-up visit for all subjects in this study will be scheduled for 30 days \pm 14 days after the MRI procedure. The follow-up visit will be conducted in the clinic and data collection will include:

- For subjects with a full DBS system implanted (includes subjects in the full system configuration group and subjects in the leads-only group who had an IPG implanted and connected to at least one lead after the MRI procedure):
 - o Success or failure to 'turn on/off' functionality of the stimulation

Clinical Investigation Plan

- o Success or failure to make adjustments to the stimulation amplitude
- o Success or failure of device interrogation and download of IPG parameters
- Success or failure to obtain lead impedance measurements (only if the Clinician Programmer is being used to interrogate the IPG)
- Adverse events
- Protocol deviations (if applicable)
- Withdrawal (if applicable)
- Device deficiency (if applicable)
- Product out of service data (if applicable)

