11.3 Source Documentation

Regulations and GCP require the Investigator to maintain information in the subject's original medical records that corroborates data collected on the CRFs. In order to comply with these regulatory requirements/GCP, the following information should be included in the subject record at a minimum and if applicable to the clinical investigation:

- Medical history/physical condition of the subject before involvement in the clinical investigation sufficient to verify CIP entry criteria
- Dated and signed notes on the day of entry into the clinical investigation referencing the Sponsor, CIP number, subject ID number and a statement that informed consent was obtained
- Dated and signed notes from each subject visit (for specific results of procedures and exams)
- Adverse events reported and their resolution, including supporting documents, such as discharge summaries, office notes and any other pertinent patient's records, including documentation of site awareness of SAEs and of investigator assessment of device relationship for SAEs
- Subject's condition upon completion of or withdrawal from the clinical investigation
- Any other data required to substantiate data entered into the CRF

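### Protocol 5.5 lets a scanned subject be declared lost without any express enquiry to third parties or records about non-fatal primary-endpoint events

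*Protocol*

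**What the plan says.** **Close-out rule (Protocol 5.5).** The general duty is to make all "reasonable efforts to locate and communicate with the subject (and document these efforts in the source documents), including the following" steps: "A minimum of two telephone calls on different days over the specified follow-up windows to contact the subject", then a letter. If the 1-month visit is missed and the attempts at communication "with the subject are unsuccessful, the subject will be considered lost-to-follow-up". A note then says what is not contact: "Telephone contact with General Practitioner, non-clinical investigation neurologist or relative without the presence of the subject", and likewise "indirect documentation obtained via discharge letters will not be considered as subject contact".

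**What is kept afterwards.** Section 5.5 lists loss to follow-up among the reasons for discontinuation. It stops data recording after withdrawal, "except for the status (deceased/alive) at the time of withdrawal, if not previously collected". Section 7.4.1 ends safety surveillance when participation ends.

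**Other routes for an event to be recorded.** Section 7.4.1 makes serious adverse events (SAEs) reportable within 3 calendar days of site awareness, and section 7.4.4 covers deaths. Section 11.3 puts in the subject record "Adverse events reported and their resolution, including supporting documents, such as discharge summaries". Section 6.3.2 collects adverse events straight after the scan.

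**Visit and analysis.** There is one follow-up visit, and section 6.4.1 says "The follow-up visit will be conducted in the clinic and data collection will include" adverse events. Protocol 8.2.1 defines the primary population by consent, MRI eligibility and a study MRI; completed follow-up is not listed. SAP 2.3.1 requires an event rate below 7% in each configuration group. SAP 2.9 plans no imputation and SAP 2.13 no sensitivity analysis.

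**The concern.** Protocol 8.2.1 gives as examples of endpoint events symptomatic intracranial hemorrhage and new permanent neurological symptoms. Either could put a subject in another hospital, unable to take a call, answer a letter or attend a clinic. Every prescribed tracing step is directed to the subject, so the steps may fail most readily in the subjects whose outcome matters most. Events of that kind would often leave a trace with a relative, a general practitioner or a hospital, and those are the sources the site is not told to ask.

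At stake is a pass/fail conclusion on safety in two groups of about 35. A missed event lowers the observed rate, and the analysis has no step that would show how far the result depends on subjects who were lost.

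**Working it through.** **1. The plan's own number.** Two groups of about 35 give 70. With 5% attrition (Protocol 5.8), 70/0.95 = 73.7, rounded up to 74, which matches the stated enrolment. In the other direction, 74 × 0.95 = 70.3. The 5% is therefore used up in going from enrolled subjects to about 35 per group. It does not describe loss after the scan, for which the documents give no figure.

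**2. The route through the text.** Take a scanned subject who has a non-fatal endpoint event at home and is admitted elsewhere.
- The calls and letter go unanswered and the visit is missed, so 5.5 classes the subject as lost.
- If the site has heard of the event by then, 7.4.1 makes it reportable and 11.3 accepts the discharge summary as support.
- If the site has not heard, no sentence tells it to ask. After close-out only vital status is recorded.
- Under 8.2.1 the subject appears to stay in the denominator as a non-event.

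**3. The decision cut.** The criterion is x/n < 7% in each group. At n = 35, 2/35 = 5.7% passes and 3/35 = 8.6% fails. The cut between 2 and 3 is the same for every n from 33 (2/33 = 6.1%, 3/33 = 9.1%) to 37 (2/37 = 5.4%, 3/37 = 8.1%).

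**4. How many lost subjects could reverse a pass, at n = 35.**

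| Observed events | Lost subjects needed, if each had an event | Rate as reported | Rate with those events |
|---|---|---|---|
| 2 | 1 | 2/35 = 5.7% | 3/35 = 8.6% |
| 1 | 2 | 1/35 = 2.9% | 3/35 = 8.6% |
| 0 | 3 | 0/35 = 0% | 3/35 = 8.6% |

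This does not depend on how the blacked-out population text in SAP 2.1.1 treats lost subjects. If they were excluded instead, the reported rates would be 2/34 = 5.9%, 1/33 = 3.0% and 0/32 = 0%, which all still pass.

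**5. Illustration of incomplete capture.** Let p be the true rate and a the share of true events that are captured. Both are assumptions; the documents give neither. With independent subjects, the chance that one group passes is P(X ≤ 2) for X ~ Binomial(35, p × a).

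| True rate p | a = 100% | a = 90% | a = 75% | a = 50% |
|---|---|---|---|---|
| 7% | 55% | 62% | 72% | 88% |
| 10% | 31% | 38% | 51% | 75% |
| 15% | 9% | 13% | 23% | 51% |

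The column a = 90% means that one event in ten falls in a subject closed as lost and is never found. The lower capture rates are outer bounds, not expectations.

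**The case against.** **The note is not the defect.** A reader might infer that it forbids using a relative's report or a discharge letter. It does not. It defines subject contact, it excludes a relative or general practitioner only when the subject is absent, and 11.3 accepts discharge summaries as adverse-event support. It also usefully stops a site from treating a relative's call as contact with the subject. This stands.

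**Outcome checks exist.** A reader might infer that a lost subject gets no outcome check at all. The documents do not support that. Vital status is kept, and SAEs and deaths are reportable once the site is aware of them. The CEC also reviews events identified by safety personnel (10.9.1). Adverse events, and device function in the full-system group, are checked immediately after the scan. What remains is the later, non-fatal event that nobody has told the site about.

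**The listed steps are a floor.** The duty is all reasonable efforts, and a diligent site might ask the family or the hospital. That is true, but the stated aim is to find and speak to the subject, not to establish the outcome.

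**Two lost subjects per group is not a planned figure.** A reader might apply the 5% to the 35 per group (35 × 0.05 = 1.75, about 2) and conclude that a failing group would be reported as passing. Step 1 of the working shows that this counts the 5% twice. The scenario also needs one observed event and both lost subjects to have events meeting all three conditions in 8.2.1. It is possible, but not predicted.

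**Subjects reached by telephone.** A reader might infer that someone who answers but cannot attend is also closed as lost. Close-out at 1 month requires that communication failed, and an adverse event told to the site by telephone is reportable under 7.4.1. The protocol is merely silent on whether that call can serve as the 1-month assessment.

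**Unseen material.** The consent pages are not in the public copy, and the case report form and monitoring plan appendices show no content. They may already prompt for outside records. Nor does any passage show that loss is in fact more frequent after an event; that is a plausible mechanism only.

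**Conclusion.** The point holds as a narrow gap. Before a scanned subject is declared lost, no step expressly requires an enquiry to third parties or records about non-fatal primary-endpoint events. After close-out, no data other than vital status are recorded.

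How often this would happen cannot be estimated from the documents. What can be shown is how little it would take: one missed event among three true events in a group turns a failure into a pass. With no scanned subjects lost, the gap has no effect.

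The conclusion rests on reading loss to follow-up as a form of withdrawal under 5.5, and on Protocol 8.2.1 for the denominator because the SAP text is blacked out. It does not invalidate the design. The missing information could largely be obtained at source, so the change is worth making.

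**What to change.** Keep the note in Protocol 5.5 as the definition of subject contact, and add the following:

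- Before a scanned subject is declared lost, the site makes and documents an enquiry to the general practitioner, the treating hospital, discharge documents or a relative, within consent and privacy rules.
- The enquiry covers SAEs, device replacement and vital status through 1 month after the MRI.
- Findings go on the adverse event form, flagged by source, and to the CEC.
- The report gives the number of scanned subjects lost in each configuration group, so that a reader can apply the reversal table above.

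Optionally, state that when a subject is reached by telephone but cannot attend, the 1-month adverse event assessment is taken on that call and the missed clinic visit is recorded as a deviation.

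The cost is a protocol wording change, possibly a matching line in the consent form (which could not be checked here), and a call or records request for each subject about to be closed as lost. Third-party reports carry less detail than a clinic assessment, which is why the source should be flagged.
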